4.3. Enrollment Criteria

Subjects will be enrolled into the study provided they have signed an informed consent document to participate in the study, have undergone all screening procedures as required, and have met all inclusion and exclusion criteria for participation in the study at Baseline/Day 1. Subjects will be assigned a subject identification number that will be retained throughout the study.

4.4. Life Style Guidelines

In order to participate in the study, subjects must be made aware of the following life style guidelines and restrictions that apply during and after the study period. Details of these life style guidelines are provided in the sections as noted.

- On designated study visit days, comply with fasting requirements for at least 9 hours prior to visit (See [Section 6](#)).

- On study visit days, do not smoke or ingest caffeine (eg, tea, coffee, some soft drinks/colas/energy drinks and power bars) during the 30 minutes prior to blood pressure and pulse (heart) rate measurements.
- On study visit days, showering or bathing is permitted prior to attending the study visit, but do not moisturize.
- Avoid vaccinations with live or attenuated live vaccines and contact with individuals who have recently received live or attenuated live vaccines (See [Section 4.4.2](#)).
- Discontinue and avoid using certain medications and treatments used to treat PsA or psoriasis (see [Inclusion Criteria](#) and list of prohibited medications [Appendix 3](#)). Discontinue and avoid using certain other prohibited medications and treatment (see [Appendix 3](#)) not used to treat PsA or psoriasis. For a medical condition in which it is important for the subject's safety to continue using the prohibited drug, and there is no study-permitted alternative, the subject must not participate in this study.
- Contact the study site investigator if there are any changes or additions to concomitant medications.
- Avoid having elective surgery (See [Section 4.4.5](#)).
- Agree to use highly effective contraceptive methods per [Section 4.4.6](#).

4.4.1. Non-Pharmacologic Interventions

The subject should continue all non-pharmacological therapies, such as physical therapy, as indicated.

4.4.2. Vaccine Guidelines

4.4.2.1. Subject Vaccination

Vaccination with any live vaccine (whether attenuated or not) is prohibited during the study and for 6 weeks after last dose of study drug. Vaccines that are allowed would include: inactivated, subunit, toxoid and DNA. It is recommended that subjects be up to date on vaccinations prior to enrollment in this study.

4.4.2.2. Household Contact with Others Vaccinated

During the study and for 6 weeks following the last dose of study drug, subjects should avoid routine household contact with children or adults who have been vaccinated with live or attenuated live vaccines. Some of these vaccines include varicella ("chickenpox") vaccine, oral polio vaccine, and the inhaled flu vaccine. Following vaccination with live component vaccines, the virus may be shed in bodily fluids, including stool, and there is potential risk that the virus may be transmitted. General guidelines suggest that exposure should be avoided following vaccination with these vaccines for the stated period:

- a. Varicella or attenuated typhoid fever vaccination for 4 weeks following vaccination;

- b. Oral polio vaccination for 6 weeks following vaccination;
- c. Attenuated rotavirus vaccine for 10 days following vaccination;
- d. FluMist[®] (inhaled flu vaccine) for 1 week following vaccination.

4.4.3. Dietary Supplements

For the purposes of this protocol, dietary supplements are defined as vitamins, minerals, purified food substances, and herbals with pharmaceutical properties.

Vitamins, minerals and purified food substances are allowed in amounts not known to be associated with adverse effects (such as hypervitaminosis). Herbals with pharmaceutical properties are allowed only if there is acceptable evidence of no CYP3A inhibition or induction. Otherwise, herbals with pharmaceutical properties must be discontinued for at least 4 weeks prior to first dose of study drug, unless there is sufficient data available regarding the duration of an herbal medication's pharmacokinetic and pharmacodynamic effects to allow a shorter washout to be specified (eg, 5 half-lives). Please direct any questions to the Sponsor.

Glucosamine sulfate and chondroitin sulfate are allowed in the study but should be stably dosed beginning at least 1 week prior to first dose of study medicine.

4.4.4. Fasting Visit Requirements

On visit days when fasting lipid panels are scheduled to be collected, all subjects should refrain from all food and liquids (water and medications permitted, if appropriate) for at least 9 hours prior to scheduled safety laboratory tests. Visits that require fasting are Baseline (if subject enrolls in A3921092 >14 days after end of qualifying study visit), Month 3, Month 6 and every 6 months thereafter, End of Treatment/Early Termination Visit and Follow-Up Visit (if required).

4.4.5. Elective Surgery

During the course of this trial, no elective surgery should be scheduled without first consulting the Pfizer Clinician.

Subjects who do require surgery should temporarily discontinue study drug for one week prior to the surgical procedure and remain off study drug after the surgical procedure until sutures/staples are removed. If absorbing sutures or chemical closure methods are utilized, study drug can be resumed when the operative site is sufficiently healed and risk of infection is minimal.

4.4.6. Contraception

4.4.6.1. Contraceptive Methods in Women of Childbearing Potential

Administration of tofacitinib in preclinical studies was shown to have teratogenic effects on the offspring of treated rats and viability of their fetuses. Due to this hypothetical risk, women of childbearing potential will not be administered tofacitinib until pregnancy is excluded and should use a highly effective method(s) of contraception during therapy with

tofacitinib and for at least one ovulatory cycle after study treatment is discontinued. They must have a negative urine pregnancy test at the baseline visit prior to the first dose of study drug and at every visit during the study (or more frequently if required by local practices), if a menstrual cycle is missed, or if potential pregnancy is otherwise suspected or if the subject has become sexually active.

For the purposes of this protocol, female subjects must either use adequate contraception or be of non-childbearing potential. The investigator, in consultation with the subject, will select an appropriate method(s) of contraception for women of child-bearing potential who are sexually active from the permitted list of contraception methods, and instruct the subject in their consistent and correct use. The investigator, at each study visit, will confirm and document consistent and correct use. In addition, the investigator will instruct the subject to call immediately if a selected birth control method(s) is discontinued or if pregnancy is known or suspected. Subjects in the United Kingdom that are women of childbearing potential are required to use two highly effective methods of birth control. Subjects in Canada who are women of childbearing potential, and sexually active, are required to use one highly effective method and one additional effective method of contraception (see [Appendix 9](#)).

Highly effective methods of contraception are those that, alone or in combination, result in a failure rate of less than 1% per year when used consistently and correctly (ie, perfect use) and include:

1. Established use of oral, injected, injected or implanted hormonal methods of contraception are allowed provided the subject remains on the same treatment throughout the entire study and has been using that hormonal contraceptive for an adequate period of time to ensure effectiveness.
2. Correctly placed copper containing intrauterine device (IUD) or intrauterine system (IUS).
3. Male condom or female condom used WITH a spermicide (ie, foam, gel, film, cream, suppository). For countries where spermicide is not available or condom plus spermicide is not accepted as highly effective contraception, this option is not appropriate.
4. Sterilization of male partner with appropriately confirmed absence of sperm in the post-vasectomy ejaculate.
5. Bilateral tubal ligation or bilateral salpingectomy or bilateral tubal occlusive procedure (provided that occlusion has been confirmed in accordance with the device's label).

NOTE: Sexual abstinence, defined as completely and persistently refraining from all heterosexual intercourse (including during the entire period of risk associated with the study treatments) may obviate the need for contraception ONLY if this is the preferred and usual lifestyle of the subject.

4.4.6.2. Women of Non-Childbearing Potential

Female subjects of non-childbearing potential must meet **at least one of the following criteria**:

- Have undergone documented hysterectomy and/or bilateral oophorectomy;
- Have medically confirmed ovarian failure; or
- Achieved post-menopausal status defined as: cessation of regular menses for at least 12 consecutive months with no alternative pathological or physiological cause; status may be confirmed by having serum follicle stimulating hormone (FSH) level within the laboratory's reference range for post-menopausal females.

All other female subjects (including females with tubal ligations) will be considered to be of childbearing potential.

4.4.7. Contraceptive Methods in Male Subjects

Administration of tofacitinib in preclinical trials demonstrated no effects on male sperm or offspring in any studies conducted to date. No effect on human male fertility is expected and male subjects need not take contraceptive precautions unless required by other concomitant medications (eg, methotrexate).

4.5. Sponsor Qualified Medical Personnel

The contact information for the sponsor's appropriately qualified medical personnel for the trial is documented in the study contact list that is located in the study portal.

To facilitate access to appropriately qualified medical personnel on study related medical questions or problems, subjects are provided with a contact card. The contact card contains, at a minimum, protocol and investigational compound identifiers, subject study number, contact information for the investigational site and contact details for a contact center in the event that the investigational site staff cannot be reached to provide advice on a medical question or problem originating from another healthcare professional not involved in the subject's participation in the study. The contact number can also be used by investigational staff if they are seeking advice on medical questions or problems, however it should only be used in the event that the established communication pathways between the investigational site and the study teams are not available. It is therefore intended to augment, but not replace, the established communication pathways between the investigational site and study team for advice on medical questions or problems that may arise during the study. The contact number is not intended for use by the subject directly and if a subject calls that number, they will be directed back to the investigational site.

5. STUDY TREATMENTS

For the purposes of this study, and per International Conference on Harmonisation (ICH) guidelines, investigational product is defined as a pharmaceutical form of an active ingredient or placebo being tested or used as a reference/comparator in a clinical trial, including a product with a marketing authorization when used or assembled (formulated or packaged) in a way different from the approved form, or when used for an unapproved indication, or when used to gain further information about an approved use (ICH E6 1.33).

Study drug will be dispensed to subjects to self-administer after appropriate training and specific written instructions are provided. Tofacitinib will be taken orally 5 mg BID (approximately every 12 hours). The investigator has the option to increase the dose to 10 mg BID in those subjects who are receiving 5 mg BID and, in the investigator's opinion, has PsA symptoms that are not adequately controlled. Changes in the dose are only permitted at scheduled study visits, unless a reduction to 5 mg BID is required due to safety abnormalities as outlined in [Appendix 4](#). Study treatment will continue in the LTE portion of the study until the subject discontinues from the study or has received approximately 3 years (36 standardized 4-week months) of treatment.

5.1. Allocation to Treatment

Subjects who enroll in this study from qualifying studies will first receive tofacitinib 5 mg BID, administered orally, in open-label dosing. Allocation of subjects to treatment will proceed through the use of an interactive response technology (IRT) system (interactive Web-based response (IWR)). The site personnel (study coordinator or specified designee) will be required to enter or select information including but not limited to the user's identification (ID) and password, the protocol number, and the subject's number. The site personnel will then be provided with a randomization number and container number(s) when investigational product is being supplied via the IRT system. The IRT system will provide a confirmation report containing the subject number, randomization number and container number(s) assigned. The confirmation report must be stored in the site's files.

5.2. Breaking the Blind

This is an open-label study. Assignment to tofacitinib will be open to the Investigator, subjects and Pfizer study team.

5.3. Drug Supplies

Each tofacitinib bottle will be labeled as appropriate for this open-label study. Study medication will be taken according to the instructions provided to the subject. The specific subject instructions will also direct the subject to bring the study medication bottle(s) to the clinic on study visit days. Any permitted dose adjustments that may occur between scheduled study visits (ie, dose reduction for safety reasons) must be clearly documented on the subject's chart and verified for start date and dose when the subject returns for their next scheduled visit.

5.3.1. Preparation and Dispensing

Tofacitinib medication will be dispensed in bulk bottles. At each dispensing visit, subjects will receive a sufficient quantity of study drug to last until their next scheduled dispensing visit. For subjects who are taking 5 mg BID, one bottle of study drug will be dispensed at each dispensing visit. If a subject is receiving 10 mg BID, 2 bottles will be dispensed. At all study visits, subjects must return all containers and unused study medications for accountability and the amount of study drug returned will be recorded.

5.3.2. Administration

Tofacitinib should be administered orally, twice daily, approximately 12 hours apart, once in the morning and once in the evening. Subjects receiving 5 mg BID will receive 1 tablet in the morning and 1 tablet in the evening. Subjects receiving 10 mg BID will receive 2 tablets in the morning and 2 tablets in the evening. Tofacitinib may be administered with or without food. If a tofacitinib dose is missed and the interval to the next scheduled dose is less than 6 hours, the missed dose of tofacitinib should not be administered. Subjects should be instructed to document any missed doses.

5.3.3. Compliance

Subject compliance with dosing administration will be verified by accounting of returned containers and trial medication at each visit.

Compliance for the tablets will be monitored by the accounting of unused medication and will be documented. Subjects who demonstrate <80% compliance should be counseled by the investigator or designee and ensure steps are taken to improve compliance. Subjects who are <80% compliant with dosage regimen for any two consecutive visit periods should be withdrawn from the study.

If the subject is over-compliant with study drug (intentional or accidental) the investigator or designee is to counsel the subject and ensure correct understanding of the study drug dosing regimen. The investigator should contact the Pfizer Study Clinician promptly with any over-compliance (>120% in a visit period) that may potentially impact the safe use of study drug or that may result in a serious adverse event.

5.4. Drug Storage

The investigator, or an approved representative (eg, pharmacist), will ensure that all investigational product, including any comparative agents and/or marketed products are stored in a secured area with controlled access under recommended storage conditions and in accordance with applicable regulatory requirements.

Investigational product should be stored in its original container and in accordance with the drug label. See the drug label for storage conditions of the product.

Storage conditions stated in the single reference safety document (SRSD), ie Investigator's Brochure (IB) will be superseded by the storage conditions stated in the labeling.

Site systems must be capable of measuring and documenting (for example, via a log), at a minimum, daily minimum and maximum temperatures for all site storage locations (as applicable, including frozen, refrigerated and/or room temperature products). This should be captured from the time of investigational product receipt throughout the study. Even for continuous monitoring systems, a log or site procedure which ensures active daily evaluation for excursions should be available. The operation of the temperature monitoring device and storage unit (for example, refrigerator), as applicable, should be regularly inspected to ensure it is maintained in working order.

Any excursions from the product label storage conditions should be reported to Pfizer upon discovery. The site should actively pursue options for returning the product to labeled storage conditions, as soon as possible. Deviations from the storage requirements, including any actions taken, must be documented and reported to the sponsor.

Once an excursion is identified, the investigational product must be quarantined and not used until the sponsor provides documentation of permission to use the investigational product. It will not be considered a protocol deviation if Pfizer approves the use of the investigational product after the temperature excursion. Use of the investigational product prior to Pfizer approval will be considered a protocol deviation. Specific details regarding information the site should report for each excursion will be provided to the site.

Site staff will instruct subjects on the storage requirements for take home investigational products.

5.5. Drug Accountability

The investigator's site must maintain adequate records documenting the receipt, use, loss or other disposition of the investigational product supplies. To ensure adequate records, all investigational product supplies will be accounted for in the drug accountability inventory forms as instructed by Pfizer and will be monitored by the accounting of unused investigational product returned by the subjects. All study drug bottles must be returned to the investigator by the subject and the investigator will return the bottles to Pfizer. At the end of the clinical study, all drug supplies unallocated or unused by the subjects must be returned to Pfizer or its appointed agent, or destroyed in an approved manner unless otherwise authorized by Pfizer. In either case, the forms must identify the study drug, including batch or code numbers, and account for its disposition on a subject-by-subject basis, including specific dates and quantities. The forms must be signed by the individual who dispensed the drug.

5.5.1. Destruction of Investigational Product Supplies

The sponsor or designee will provide guidance on the destruction of unused investigational product (eg, at the site). If destruction is authorized to take place at the investigator site, the investigator must ensure that the materials are destroyed in compliance with applicable environmental regulations, institutional policy, and any special instructions provided by Pfizer, and all destruction must be adequately documented.

For all containers returned to the investigator by the subject, the investigator will maintain the returned supply until destruction is authorized or release to a third party for destruction is granted.

5.6. Concomitant Treatment(s)

It is important to be aware of, and document, **all** concomitant treatments including: prescription, non-prescription (ie, over-the-counter) and herbal medications.

A subject who is receiving an allowed concomitant medication for any reason must be on a locally-approved medication and dose that is considered standard-of-care for the treated indication, and this must be documented in the case report form. Subjects are not allowed to receive any other investigational drug during the study.

It is recommended that subjects avoid changing non-prohibited prescription or non-prescription drugs, vitamins, and dietary supplements within 7 days or 5 half-lives (whichever is longer) prior to the first dose of study medication and prior to study visits unless otherwise noted below, throughout the study.

Treatments that are taken in the Screening period (after informed consent is obtained and before the first dose of study drug) will be documented as prior treatments. Treatments taken after the first dose of study drug has been administered will be documented as concomitant treatments. All concomitant treatments taken during the study must be recorded in the study records with indication (as appropriate), daily dose and start and stop dates of administration. Subjects will be queried about concomitant treatments at each study visit.

Minimum guidelines for folate supplementation during study: Subjects on methotrexate **must** receive folate supplementation according to local methotrexate label guidelines and standard of care. A minimum of 5 mg weekly based on folic acid should be given unless local guidelines or standard of care state otherwise.

5.6.1. Stable Background Pain or Other Arthritis Therapy

Use of background medication (eg, methotrexate, leflunomide or sulfasalazine) by a subject is not a requirement. However, if used, the concomitant DMARD should be the same medication as the subject was receiving in the qualifying study. Adjustment of background medications are allowed for reasons of inadequate efficacy of current treatment, or may be tapered or discontinued due to disease improvement. Adjustments for safety reasons may be done at any time, but if this leads to changes in excess of those allowed, the investigator must receive approval from the Pfizer Clinician to allow the subject to continue in the trial. Dose adjustments of the permitted concomitant DMARDs should not occur any more frequently than every 3 months. If adjustment of the concomitant DMARD is required for safety, it can occur at any time. If the concomitant DMARD requires adjustment for efficacy, it should be completed at the visit or within 14 days.

If a concomitant DMARD is discontinued during the course of the study, it should not be re-initiated. Addition of any new concomitant DMARD is not allowed; subjects are only permitted to receive one concomitant DMARD in the study.

Dose adjustments may be made, or background NSAID/COX-2 inhibitors may be switched, but should be no more frequently than every 3 months, and should be more than 14 days prior to a study visit. Oral corticosteroid dose should not exceed 10 mg prednisone or its equivalent daily. Daily dosage of NSAIDs/COX-2 inhibitors and corticosteroids must not be modified within the 24 hours prior to any study visit, except if adjustment is needed to protect a subject's safety.

Methotrexate doses may be adjusted no more frequently than every 3 months (and remaining ≤ 20 mg/week). Adjustments should not be made more than 4 weeks prior to a study visit. Intra-articular steroids should be administered in a total dosage of no more than 80 mg of methylprednisolone or equivalent every 6 months. Intra-articular hyaluronate sodium injections may be administered for indications in accordance with the local label. Injected joints will be considered to have their pre-injection status for efficacy assessments during the remainder of the study. Intra-articular injections should be administered more than 6 weeks prior to a study visit (See [Appendix 6](#)).

The total daily dose of acetaminophen may not exceed 2.6 grams per day, and the total daily dose of opioid may not exceed the potency equivalent of 30 mg of orally-administered morphine (See [Appendix 5](#), [Appendix 6](#)).

Daily dosage of opioids and acetaminophen/paracetamol must not be modified within the 24 hours prior to any study visit, except if adjustment is needed to protect a subject's safety.

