4.1.1. Inclusion Criteria That Apply to All Subjects

1. Evidence of a personally signed and dated informed consent document indicating that the subject (or a legal representative) has been informed of all pertinent aspects of the study.
2. Subjects who are willing and able to comply with scheduled visits, treatment plan, laboratory tests, and other study procedures.
3. Subjects must have a diagnosis of PsA and previously completed participation in a qualifying study of tofacitinib for the treatment of PsA or have required earlier discontinuation of treatment in a qualifying study for reasons other than treatment-related adverse events (exception being injection-related AEs) with the written approval of the Pfizer Clinician.
4. Subject must be at least 18 years of age (20 years old for subjects in Taiwan) or older at the Screening visit.
5. Subjects receiving permitted traditional non-biologic background DMARDs, eg, methotrexate, sulfasalazine or leflunomide, must be dosed in accordance with the local regulatory label.

All local standard of care practices for administration of non-biologic background DMARD therapy, including laboratory testing, contraceptive requirements, follow-up care and contraindications, should be performed according to the local standards of care throughout the study.

- Methotrexate: Maximum dose of 20 mg/week. Minimum duration of therapy 4 months and dose stable for 4 weeks prior to first dose of study drug. Subjects on methotrexate should be on an adequate and stable dose of folate supplementation (not less than 5 mg weekly based on folic acid, unless such doses would violate the local label guidelines or standard of care) for at least 4 weeks prior to the first dose of study drug (see [Section 5.6](#)). Subjects must

not have had previous serious toxicity while on methotrexate and not be expected to require evaluation for possible methotrexate toxicity (eg, require a liver biopsy for methotrexate toxicity) during the study.

- Sulfasalazine: Maximum dose of 3 gm/day. Minimum duration of therapy 2 months and dose stable for 4 weeks prior to first dose of study drug.
 - Leflunomide: Maximum dose of 20 mg/day. Minimum duration of therapy 4 months and dose stable for 4 weeks prior to first dose of study drug.
 - Other traditional non-biologic DMARDs not listed as a prohibited concomitant medication (see [Appendix 3](#)) may be considered after discussion with the Sponsor.

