Intravenous or intramuscular corticosteroids, biologic response modifiers and DMARDs, other than methotrexate, sulfasalazine and leflunomide, are not allowed during this study. Intra-articular corticosteroids may be given in no more than two joints, in a cumulative dose of no more than 80 mg methylprednisolone or its equivalent in any 6 month study period. Intra-articular hyaluronate sodium injections may be administered for indications in accordance with the local label at least 6 months from the last hyaluronate injection in no more than two joints in any 6 month study period. Injections should be avoided for 6 weeks before any study visit. Injected joints will also be considered as having their pre-injection status (swollen and/or painful/tender) and should not be counted for the remainder of the trial.

Acetaminophen/paracetamol is not permitted as a part of combination products such as over-the-counter “cold remedies” or in combination with opioids if the acetaminophen/paracetamol dose will exceed 2.6 gm/day. Subjects who require rescue for more than 10 consecutive days should be discontinued from the trial. There is no limit to the duration of nonconsecutive use of rescue medications. In addition, subjects must not be dosed with rescue acetaminophen/paracetamol or opioids within 24 hours prior to a study visit except if adjustment is needed because subject is experiencing intolerable pain. Baseline stable acetaminophen/paracetamol or opioids should NOT be discontinued in advance of study visits.

Subjects must not be dosed with any rescue intervention within 24 hours prior to a study visit except if adjustment is needed because subject is experiencing intolerable pain.

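### The methotrexate timing sentence in Protocol 5.6.1 appears inverted: read literally, it steers non-safety dose changes into the 28 days before a study visit

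*Protocol*

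**What the plan says.** Protocol Section 5.6.1 limits methotrexate changes to one every 3 months and 20 mg/week, then adds: "Adjustments should not be made more than 4 weeks prior to a study visit". Safety changes are exempt ("Adjustments for safety reasons may be done at any time"). For a change of concomitant DMARD made for efficacy, the same section says "it should be completed at the visit or within 14 days", without saying whether the 14 days fall before or after the visit.

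The other timing rules are:

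- NSAID/COX-2 changes, Section 5.6.1: "and should be more than 14 days prior to a study visit".
- Joint injections, Section 5.6.1: "Intra-articular injections should be administered more than 6 weeks prior to a study visit". Appendix 6 restates this as "Injections should be avoided for 6 weeks before any study visit".
- Methotrexate at entry to the extension, Section 4.1.1: "Minimum duration of therapy 4 months and dose stable for 4 weeks prior to first dose of study drug".
- Methotrexate at sub-study entry, Appendix 10 Sections 4.1 and 5.1: stable dose for 4 weeks beforehand.
- Non-prohibited drugs in general, Section 5.6: a recommendation to avoid changes within 7 days or 5 half-lives, whichever is longer, before first dose and "prior to study visits unless otherwise noted below, throughout the study".

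**The concern.** A ban on changes made earlier than 4 weeks before a visit leaves only the last 4 weeks. That is the period in which a new methotrexate dose is least settled when ACR response, HAQ-DI and the other efficacy measures are taken. The NSAID and injection rules exist to prevent this, and elsewhere the protocol uses the same 4-week figure as a minimum period of stable methotrexate.

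Two things are at stake. A site that follows the sentence puts recent dose changes into the by-visit efficacy summaries; SAP Section 5.6 excludes no subject for protocol deviations, so neither following the sentence nor departing from it removes those data. A site that follows it before a Month 24 to 36 visit can also leave a subject short of the 4-week stability needed to enter the sub-study at that visit.

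**Working it through.** The plan gives no figure to reproduce. The check compares the rules and counts calendar days.

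**Inputs.** A month is 28 days (Protocol Section 6.2). Visits are at Baseline and Months 1, 3, 6, and every 3 months to Month 36 (Schedule of Activities), which gives 13 intervals: one of 28 days, one of 56 and eleven of 84. Visit windows are ±7 days at Months 1 and 3 and ±10 days later (Sections 6.2.1 to 6.2.4). Sub-study entry is at Month 24, 27, 30, 33 or 36 (Appendix 10, Section 6.1).

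**Definition.** For an interval of L days and a change on day d after a visit, lead = L − d days to the next visit. The literal rule permits lead ≤ 28. The proposed rule permits lead ≥ 28.

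| Interval | L | Between-visit days the literal rule permits | Lead for a change on days 1–14 | Days 0–14 meeting the proposed rule |
|---|---|---|---|---|
| Baseline to Month 1 | 28 | 1–27 | 14–27 | 1 of 15 (day 0) |
| Month 1 to Month 3 | 56 | 28–55 | 42–55 | 15 of 15 |
| Each of the 11 from Month 3 | 84 | 56–83 | 70–83 | 15 of 15 |

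**Stability at the next visit.** In an 84-day interval, lead ≤ 28 means d ≥ 84 − 28 = 56, so days 56 to 83 are permitted: 83 − 56 + 1 = 28 days. Only day 56 gives a full 28 days of stable dosing. The other 27 give less than 4 weeks.

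**Against the efficacy rule.** There are two readings of the 14 days.

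- After the visit: from Month 1 on, days 1–14 have leads of 42–55 or 70–83 days. All exceed 28, so the literal sentence permits none of them and the two rules conflict.
- Before the visit: the rules agree, but both then place the change in the last 14 days before an assessment.

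Visit-day changes are not in conflict, since a change made at a visit can be read as 0 days before it. Safety changes are exempt.

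**Proposed rule at the window extremes.** The shortest lead for a day-14 change, with the first visit late and the next early, is:

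- Month 1 to 3: 56 − (7 + 7) − 14 = 28 days
- Month 3 to 6: 84 − (7 + 10) − 14 = 53 days
- Month 6 onward: 84 − (10 + 10) − 14 = 50 days

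All are at least 28.

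**The case against.** The strongest reply is that little depends on this sentence. The extension's primary endpoints are safety. Efficacy is summarised descriptively, without models (SAP Section 6.4), in one cohort dosed flexibly between 5 and 10 mg BID (SAP Section 8.2), and the protocol already allows DMARD changes for poor response or improvement. The sentence says should, not must. All of this stands, and it limits the consequence to some blurring of by-visit summaries.

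Section 5.6 also discourages changes in the 7 days before a visit, and the disputed sentence, which sets only an outer limit, can be followed alongside it. Leads of 8 to 28 days would then remain: 21 days, of which 20 still give less than 4 weeks of stability. That softens the worst case without curing it. Section 5.6 is a recommendation and gives way to anything noted below it, so it shows the intended direction but does not formally override Section 5.6.1.

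On the sub-study, its own 4-week criterion governs eligibility whatever Section 5.6.1 says, no site is compelled to make a change, and a change at the preceding visit gives 84 days of stability. This also stands. The difficulty is confined to between-visit changes. A subject who misses entry at Months 24 to 33 can enter at a later visit; after Month 36 there is none.

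Finally, the conflict with the efficacy rule depends on how the 14 days are read. That is correct, but neither reading makes the section sound.

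**Conclusion.** The point holds. As written, the sentence points non-safety, between-visit methotrexate changes toward the assessment, against the comparable timing rules and the 4-week stability criteria. The documents do not show how this arose, so it is described as appearing inverted; nothing in them suggests that the literal direction was intended.

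The size is a calendar count on the nominal schedule: 27 of the 28 between-visit days permitted in an 84-day interval give less than 4 weeks of stable dosing at the next visit. How many subjects this touches is unknown. No test, analysis set or sample size changes. It should still be corrected, because it is an operative instruction to sites and a site that infers the sensible meaning departs from the written text.

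**What to change.** Make two edits in Protocol Section 5.6.1.

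1. Replace the methotrexate timing sentence with: *Except for safety reasons, methotrexate adjustments should be made at least 4 weeks before the next scheduled study visit.*
2. In the efficacy-adjustment rule, add the words *after it*, so that the 14 days clearly follow the visit.

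From Month 1 on, every day from 0 to 14 after a visit then satisfies both rules.

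The cost falls between Baseline and Month 1. Days 1 to 14 after Baseline would not meet the new methotrexate sentence, so an efficacy-driven change would have to be made on the Baseline day or wait until Month 1. A Baseline-day change has a lead of 28 days to the scheduled Month 1 visit, but 28 − 7 = 21 days if that visit takes place at the early edge of its window. This is a small restriction at the very start of the extension. No analysis or sample size changes.
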